8.6.4. Physical Examinations

Physical examination results will be presented in subject data listings.

9. CHANGES TO THE PLANNED ANALYSES

The timing of the primary efficacy analysis will be based on completion of the US 50 mg cohort. The protocol indicated the initial analysis of the primary efficacy endpoint would be performed using subjects from US and China and include country as an effect in the ANCOVA model. Given the delays in enrollment in China due to COVID-19, the primary analysis has been adjusted to only include the US cohorts and a modified ANCOVA model as described above.

The treatment group used for the presentation of data based on the mITT population has been modified from the protocol. Per the study protocol, the data were to be analyzed based on randomized treatment.

As a point of clarification and as noted for the key secondary efficacy analysis above, due to data collection precision, subjects with a reduction of at least 29.5% from baseline will count as responders. Similar conventions were used for the sensitivity analyses of that endpoint using different responder definitions.

Since one subject received the incorrect study treatment (active instead of placebo), an as-treated population (ATP) has been added to the SAP. The ATP will be used to evaluate the treatment differences in efficacy endpoints using treatment received instead of randomized treatment.

Due to the impact of COVID-19, all efficacy endpoints will be analyzed at End of Treatment and End of Study. The definition of those timepoints are described in section 3.1. Per the protocol, endpoints were evaluated at Week 12 and Week 16 but the differences in duration of treatment require further evaluation given the visits may not correspond to the number of weeks specified in the protocol visit schedule.

An additional SRC analysis was performed during the COVID-19 pandemic to confirm safety prior to allowing the option of extended 50mg cohort dosing. If additional SRC reviews are performed, they will be discussed in the CSR.

Additional supplementary and sensitivity analyses related to the protocol-planned analyses have been added to the SAP. Specifically, the absolute change from baseline in MRI-PDFF has been added in addition to the planned percent change. The change from Week 12 to Week 16 in MRI-PDFF has been added. ALT and AST normalization has been added as an additional analysis of the liver aminotransferases.

Analyses and data presentations described in the protocol have been expanded upon, but no other changes were made to analyses specified in the protocol. Any additional changes to the planned analyses as detailed in this SAP will be described in the CSR.

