5. ANALYSIS POPULATIONS/SETS

The modified intent-to-treat population (mITT) is defined as all subjects who are randomized, receive study drug for at least 8 weeks, and have a baseline and at least 1 post-baseline MRI-PDFF assessment on or after Week 8. The mITT is the primary population for analysis of MRI-PDFF assessments and subjects will be analyzed according to the randomized treatment assignment.

The intent-to-treat population (ITT) is defined as all subjects who are randomized and received at least 1 dose of study drug. The ITT will be used for analysis of a subset of secondary efficacy endpoints and supportive and sensitivity analyses of MRI-PDFF assessments. Subjects will be analyzed according to the randomized treatment assignment.

The as-treated population (ATP) is defined as all subjects who are randomized and received at least 1 dose of study drug. The ATP will be used for analysis of secondary efficacy endpoints and supportive and sensitivity analyses of MRI-PDFF assessments. Subjects will be analyzed according to the treatment received.

The safety population is defined as all subjects who are randomized and received at least 1 dose of study drug and will be used for all analysis of safety. Subjects will be analyzed according to

the treatment received. If all subjects were dosed according to randomized treatment assignment, then the safety population and ITT are identical.

A per-protocol (PP) population may be defined for sensitivity analyses of the efficacy endpoints. The PP population will be based on subjects in the mITT population with data excluded from subjects who have important protocol violations deemed to possibly affect the efficacy measurements or integrity of any other key study data. Subjects will be analyzed according to the actual treatment received. If a PP population is implemented, details on subjects excluded will be provided in the CSR.

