8.3.1.2. Additional Analyses of the Primary Efficacy Endpoint

The primary efficacy analysis will be repeated using the ITT population, ATP, and PP population. Analyses will be conducted with LOCF from Week 8 onward and repeated excluding missing data (no LOCF).

In addition to the primary analysis of Week 12 that includes all subjects who had no more than 12 weeks of study treatment, an analysis of the End of Treatment MRI-PDFF data including data from the extended dosing subjects will be performed in the mITT, ITT, ATP, and PP populations.

An analysis of MRI-PDFF data in the log scale will be performed in the mITT population. The log ratio of Week 12 to baseline [$\log(\text{Week 12}/\text{Baseline})$] will be analyzed using a similar

ANCOVA mode. In the event that model assumptions are not met for the primary efficacy analysis noted above, the analysis in the log scale will become primary.

At the time of the final analysis, the above analyses will be repeated using all data from the US and China. Subset analyses will be performed on the primary efficacy endpoints for subjects enrolled in US and China to evaluate the consistency of results between subjects enrolled in each country. The ANCOVA model will incorporate fixed effects for the stratification factor (diabetes presence/absence), country (US/China), treatment group (TVB-2640 50 mg and pooled placebo), and country-by-treatment interaction and with the baseline MRI-PDFF value as a covariate including all subjects in the mITT from US and China who received 50 mg or placebo.

A test for country-by-treatment interaction will be performed. If there is no interaction detected ($p \geq 0.05$), the primary efficacy endpoint, percent change from baseline in hepatic fat fraction at Week 12, as determined by MRI PDFF, will be analyzed using an ANCOVA model with fixed effects for the stratification factor (diabetes presence/absence) and treatment group (i.e., TVB-2640 dose groups and pooled placebo) and with the baseline MRI-PDFF value as a covariate including all subjects from US and China (with no fixed effect for country). If the country-by-treatment interaction is significant ($p < 0.05$) then a separate analysis will be performed on subjects enrolled in China in the 50 mg cohort. This analysis is not powered to detect a significant difference but would be supportive/descriptive in nature to evaluate trends.

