Similar responder analyses will be performed using response level definitions of 20%, 40%, and 50%. As done for the key secondary endpoint efficacy endpoint, subjects with a reduction of at least 19.5%, 39.5%, and 49.5% from baseline, respectively, will count as responders. Analyses will be repeated in the ITT, ATP, and PP populations. Analyses of the key secondary endpoint performed in the ATP populations will include summaries of all subjects in the analysis population, as well as the subset of subjects that have at least 8 weeks of treatment and an evaluable assessment on/after 8 weeks (i.e., the same subjects in the mITT population).

Similar responder analyses will be performed using reduction in liver fat at End of Study in the mITT, ITT, and ATP populations.

A scatter plot of End of Treatment body weight changes versus End of Treatment liver fat changes will be graphed by treatment and overall in the ATP. A subset will also be run in subjects with at least a 30% reduction in liver fat at Week 12.

In the key secondary analysis, missing Week 12 values for MRI-PDFF will be imputed with the last post-baseline observation on or after Week 8 in the mITT population. Sensitivity analyses excluding subjects with missing data will also be performed.

Other Efficacy Endpoints

Other efficacy endpoints will be summarized using the ATP. A limited set of endpoints will be repeated in the ITT.

Liver aminotransferases will be evaluated using observed values and changes from baseline by study visit. Summaries will be performed for ALT and AST and will be presented by treatment group.

The changes at 12 weeks will be summarized for each treatment group and compared between each TVB-2640 dose group and pooled placebo using a linear mixed-effects model for repeated measures (MMRM). The model will include the stratification factor (diabetes presence/absence),

Sponsor: Sagimet Biosciences

Protocol Number: 3V2640-CLIN-005

Version and Date: Final Version 1, 02June2020

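### SAP Section 9 says the mITT grouping departs from randomised assignment while SAP Section 5 keeps it; Section 9 also does not list that the as-treated set displaces ITT as main set for the non-MRI secondary endpoints

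*SAP*

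**What the plan says.** **Grouping of the mITT.** SAP Section 5 reads: "The mITT is the primary population for analysis of MRI-PDFF assessments and subjects will be analyzed according to the randomized treatment assignment". Protocol 13.2.1 has the same rule. SAP Section 9, which lists the SAP's departures from the protocol, reads: "The treatment group used for the presentation of data based on the mITT population has been modified from the protocol". Its next sentence says that the protocol's rule was randomised treatment. It gives neither the replacement rule nor a reason.

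**What rests on the mITT.** SAP 8.3.1.1 bases the primary analysis on it without restating the grouping, and SAP 8.3.2 bases the key secondary test on it. SAP 7.3 puts both endpoints, each at two doses, in one fixed sequence.

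**The mis-dosed subject.** Section 9 also says: "Since one subject received the incorrect study treatment (active instead of placebo), an as-treated population (ATP) has been added to the SAP". It goes on to say that this population evaluates efficacy by treatment received in place of randomised treatment.

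**Set for the other secondary endpoints.** Protocol 13.2.1 assigns secondary efficacy endpoints to ITT, and Protocol 13.2.2 runs their repeated-measures models there. SAP Section 5 narrows this: "The ITT will be used for analysis of a subset of secondary efficacy endpoints". SAP 8.3.2, on the non-MRI endpoints, says: "Other efficacy endpoints will be summarized using the ATP. A limited set of endpoints will be repeated in the ITT". It does not name the limited set. Section 9 closes by saying that "no other changes were made to analyses specified in the protocol".

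**The concern.** Section 9 of the SAP is not a record of superseded text. It states what this SAP does differently from the protocol, so a programmer may follow it. One who follows Section 5 keeps the mis-dosed subject in pooled placebo. One who takes Section 9 to mean treatment received moves that subject to a dose arm. Both would be following the current SAP, and the analyses affected are those under Type I error control.

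The second matter is one of listing. The main set for the non-MRI secondary endpoints, ALT and AST among them, moves from a grouping by randomisation to a grouping by treatment received. Section 9 reports that a population was added. It does not say that this population takes over ITT's place, and a reader cannot tell in advance which endpoints will also have an as-randomised result.

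**Working it through.** **Step 1: the texts side by side**

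| Place | mITT grouping |
|---|---|
| Protocol 13.2.1 | as randomised |
| SAP 5 | as randomised |
| SAP 8.3.1.1 | mITT named, grouping not restated |
| SAP 9 | changed from randomised; new rule not named |

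SAP 5 and SAP 9 conflict. For evidence of intent:

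- SAP 8.3.1.2 says: "The primary efficacy analysis will be repeated using the ITT population, ATP, and PP population". This does not settle it. The as-treated population needs only one dose, so it is wider than the mITT, and the repeat would add something under either grouping.
- SAP 8.3.2 runs the key secondary endpoint in the as-treated population a second time, limited to subjects with at least 8 weeks of treatment and "an evaluable assessment on/after 8 weeks (i.e., the same subjects in the mITT population". That run would duplicate the mITT analysis if the mITT were already grouped by treatment received. It therefore points to as randomised, but for one endpoint only.

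**Step 2: primary endpoint**

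Inputs from SAP 3.3: SD 30, difference 24, 30 evaluable per group. Assume the subject is in the analysis and has the full active effect.

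- Shift in placebo mean when kept as randomised: 24/30 = 0.8 points.
- Standard error of the difference: 30 × √(2/30) = 7.75.
- Ratio: 0.8/7.75 = 0.10.
- Expected difference: 24 × 29/30 = 23.2, a dilution of 1/30 = 3.3%.

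**Step 3: key secondary endpoint at the planned rates**

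SAP 3.3 plans for 16.7% on placebo and an increase of 36.7 points, that is 5/30 and 16/30. These inputs reproduce the plan's own figure: the exact power of Fisher's test is 80.0%, against a stated minimum of 80%. Two-sided p-values from unstratified tests:

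| Grouping | Table | Chi-square | Fisher |
|---|---|---|---|
| As randomised | 16/30 v 5/30 | 0.0029 | 0.0061 |
| As treated, subject joins compared dose, responder | 17/31 v 4/29 | 0.0009 | 0.0011 |
| As treated, subject joins compared dose, non-responder | 16/31 v 5/29 | 0.0053 | 0.0070 |
| As treated, other dose comparison, responder | 16/30 v 4/29 | 0.0013 | 0.0022 |
| As treated, other dose comparison, non-responder | 16/30 v 5/29 | 0.0038 | 0.0061 |

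Every row is significant at 0.05.

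**Step 4: how often the grouping would change the conclusion**

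All outcomes were enumerated: Binomial(30, 0.534) active responders, Binomial(29, 0.167) correctly dosed placebo responders, and one mis-dosed subject responding with probability 0.534 (16.7% + 36.7%). Each outcome was tested under both groupings.

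| Comparison | Test | Significant only as treated | Significant only as randomised | Total |
|---|---|---|---|---|
| Dose arm the subject joins | Chi-square | 4.8% | 1.9% | 6.7% |
| Dose arm the subject joins | Fisher | 8.0% | 0.7% | 8.7% |
| Other dose arm | Chi-square | 3.6% | 0.5% | 4.0% (unrounded sum) |
| Other dose arm | Fisher | 5.3% | 0.0% | 5.3% |

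The planned test is a diabetes-stratified CMH. The documents give no rates by stratum, so these unstratified figures are illustrations. They are not conditioned on both primary tests having succeeded.

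**Step 5: non-MRI secondary endpoints**

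By the SAP 5 definitions, ITT and the as-treated population have the same members and differ only in grouping. With one mis-dosed subject among 30 on placebo, the effect is diluted by about 3% as randomised. These endpoints carry no alpha.

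**The case against.** On the first matter, it can be said in the plan's favour that Section 9 speaks of presenting data, which may mean displays and not tests. It can also be said that SAP 5 may be the passage left uncorrected, since its mITT wording repeats the protocol's. Both are possible. A reader might infer that the primary analysis is really planned as treated, or that the Section 9 sentence is plainly the error. The documents support neither as a certainty: Section 9 never states an as-treated rule for the mITT, and the only real evidence for as randomised is the single run in SAP 8.3.2. The conflict stands on either reading.

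On the second matter, the objection largely succeeds. A reader might infer that the move away from ITT was concealed. It was not. Section 9 discloses the as-treated population, its reason and its use by treatment received; SAP 5 cuts ITT to a subset; SAP 8.3.2 states the order openly. Protocol 13.2.2 also leaves further detail on other secondary endpoints to the SAP, and it leaves the exploratory endpoints there altogether, so they are no part of this point. But the protocol does name ITT for the secondary endpoints. What remains is that Section 9 omits the change of main set before saying that there were no other changes, and that the ITT repeats are unnamed.

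On size, the figures depend on the subject being in the mITT and not among those whom SAP 8.3.1.1 excludes for dosing beyond 12 weeks. If either condition fails, the effect on the mITT tests is nil.

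**Conclusion.** A minor point that holds. The contradiction between SAP 5 and SAP 9 on the mITT is certain from the text; which rule was intended is not, with the balance towards as randomised. The gap on the secondary endpoints is an incomplete list of changes.

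The expected impact is small: 0.8 points on the placebo mean, or 0.10 standard errors, and no change of conclusion if the key secondary data fall at the planned rates. The illustrative 4% to 9% chance of a changed key secondary test assumes 30 per arm, planned response rates, unstratified tests, no gatekeeping, and one mis-dosed subject who is in the analysis and responds at the active rate. The documents give neither the dose that subject received nor the outcome. A reader might take 4% to 9% as this trial's risk of a wrong conclusion; with those conditions unverified, it is not that.

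**What to change.** Correct the Section 9 sentence so that SAP 5, 8.3 and 9 all say that the mITT and ITT are analysed as randomised, matching Protocol 13.2.1, with the as-treated population as sensitivity.

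For the non-MRI secondary endpoints, do one of two things:

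- keep the protocol's ITT as main set, with the as-treated population as sensitivity; or
- keep the as-treated population as main set, list the switch from ITT in Section 9 with its reason, and name the endpoints to be repeated in ITT.

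The cost is SAP wording and, under the first option, exchanging which tables are main and which are sensitivity. No new data are needed. The drawback of as-randomised grouping is about 3% dilution of the effect from one mis-dosed subject, and the as-treated sensitivity analysis would show it.

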APPENDIX 1. COVID-19 IMPACT AND DATA HANDLING

COVID-19 impacts on 3V2640-CLIN-005 include, but are not limited to, missed visits, inability to complete certain assessments per the protocol including Week 12 MRI-PDFF data which constitutes the data for the primary efficacy endpoint. In order to collect as much efficacy data on all randomized subjects, subjects were allowed to continue on their treatment beyond Week 12 and have their end of treatment MRI-PDFF performed at any time between Week 11 and Week 16 per protocol Amendment 5. Study drug was not permitted to be continued for more than 16 weeks. The End of Study Visit was scheduled for 4 weeks after the last dose of study drug.

Given the uncertainty of the impact of extended dosing beyond Week 12 on efficacy, the primary and secondary efficacy analyses will be performed excluding subjects who entered extended dosing beyond 12 weeks. Sensitivity analyses that include these subjects will be performed to evaluate the end of treatment efficacy.

The analysis of safety will include all collected data regardless of treatment extension.

An addendum to this SAP will be developed that documents all additional data handling techniques employed to manage COVID impacted data, if needed.

Sponsor: Sagimet Biosciences

Protocol Number: 3V2640-CLIN-005

Version and Date: Final Version 1, 02June2020

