- 3 Serum beta-human chorionic gonadotropin (β -HCG) pregnancy testing is to be performed for all female subjects of child-bearing potential during screening and serum or urine β -HCG pregnancy testing is to be performed within 48 hours before first dose on Day 1; subjects with positive results are not eligible for study participation. Pregnancy testing is to be repeated during the study any time pregnancy is suspected; study drug is to be discontinued for any subject with a positive result.
- 4 Results of liver biopsy conducted within 24 months before randomization, with findings consistent with NASH diagnosis, must be collected and documented.
- 5 If prior biopsy was not performed or is not available, subjects must have a suspected diagnosis of NASH based on clinical presentation/historical assessments (see protocol [Section 8.2](#)) and must have MRE ≥ 2.5 kpa (Cohorts 1 and 2 only) and MRI-PDFP $\geq 8\%$ during screening.
- 6 Screening serologies include HIV RNA, HBsAg, anti-HCV, and HCV RNA. Subjects with positive anti-HCV who test negative for HCV RNA at screening will be allowed to participate in the study. A PCR test for SARS-Cov-2 (the virus that causes COVID-19) also is to be performed; subjects with positive results are not eligible for study participation.
- 7 ECGs are to be performed before and 4 hours after the first study drug dose on Day 1.
- 8 Vital signs include oral temperature and supine pulse, systolic/diastolic blood pressure, and respiration rate. Measurements are to be made after the subject has been resting in a supine position for a minimum of 5 minutes.
- 9 Slit lamp and near and far visual acuity testing is to be performed. Baseline examinations may be performed within 28 days before Day 1. If a subject experiences a treatment-emergent ophthalmologic abnormality, an ophthalmologic examination should be performed within 24 to 48 hours or next business day after symptom onset to evaluate the abnormality.
- 10 Hematology parameters include hemoglobin, hematocrit, platelet count, red blood cell (RBC) count, white blood cell (WBC) count with differential, and absolute neutrophil count (ANC), and prothrombin time (PT), international normalized ratio (INR), and activated partial thromboplastin time (aPTT) and fibrinogen.
- 11 Liver aminotransferases include AST and ALT. Liver aminotransferases collected as part of the clinical chemistry panel for safety are also applicable for efficacy assessments.

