The Sponsor notes that the coronavirus disease-2019 (COVID-19) pandemic may impact the conduct of the 50 mg and 75 mg cohorts, with challenges potentially arising from quarantines and travel limitations affecting study subjects as well as clinic and imaging facility closures. Accordingly, safety assessments scheduled for the Week 12 and 16 visits, as identified in [Table 2](#), including sample collection for clinical laboratory tests, physical examinations, and documentation of adverse events (AEs), may be performed at an alternate study center or by home health care visit. Furthermore, if the subject is unable to attend the Week 12 visit at the study center, one MRI-PDFF may be performed at any time between Week 11 and 16. If this scan is performed after Week 12, the subject must continue to receive study drug until the final scan is performed; however, study drug is not to be continued for >16 weeks. The safety of subjects who continue dosing beyond 12 weeks will be assessed during this continued dosing period by planning for blood sample collection at an alternate site or home visit at Week 12 and blood sample collection and physical examination on the last day of dosing. A 4-week off treatment safety assessment is to occur after the last dose, regardless of whether a subject receives treatment for 12 or 16 weeks.

In Cohorts 1 and 2, study drug will be dispensed to subjects in a single-blinded fashion. All other study personnel, with the exception of personnel conducting/interpreting imaging studies (see [Section 11.1](#)) at each study center, will be unblinded to the subject's treatment assignment. In Cohort 3, study drug will be dispensed in an open-label fashion.

Efficacy variables include MRI-PDFF as well as measurement of liver aminotransferases, lipid parameters, and markers of NASH and liver fibrosis. The primary endpoint is percent change from baseline in liver fat from baseline at Week 12, as determined by MRI-PDFF. The percentage of subjects with at least a 30% reduction in the primary endpoint is a key secondary efficacy endpoint.

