The primary and key secondary efficacy analyses will be conducted using a fixed-sequence strategy to maintain the overall Type I error rate at 0.05. The primary efficacy analyses will compare the primary efficacy endpoint between each randomized TVB-2640 dose group with the pooled placebo group, each using a 2-sided test at the 0.05 level of statistical significance with the goal of identifying the minimum effective dose. The primary efficacy analyses start with the highest dose-group comparison and if statistically significant, testing will proceed to the low dose group comparison. If both comparisons of the primary efficacy endpoint are significant, then testing will proceed to the key secondary efficacy analyses. The key secondary efficacy analyses will similarly compare the key secondary efficacy endpoint between each randomized TVB-2640 dose group with pooled placebo group, each using a 2-sided test at the 0.05 level of statistical significance. The key secondary efficacy analyses start with the highest dose-group comparison and if statistically significant, testing will proceed to the low dose group comparison.

In the primary and key secondary analyses, missing Week 12 values for MRI-PDFF will be imputed with the last post-baseline observation on or after Week 8 in the mITT. Secondary and sensitivity analyses using other methods for missing data methods and in different analysis populations will be described in the SAP.

For other continuous secondary efficacy endpoints measured at multiple post-baseline visits, the changes at 12 weeks will be summarized for each treatment group and compared between each randomized TVB-2640 dose group and pooled placebo using a linear mixed-effects model for repeated measures in the ITT. The model will include the stratification factor (diabetes

presence/absence), treatment group, visit, and treatment-by-visit interaction as the fixed effects, and baseline value as a covariate using an unstructured variance-covariance matrix. The point estimates for the least-squares mean of the pairwise difference for each randomized TVB-2640 dose group and pooled placebo comparison at each visit and the corresponding 95% confidence interval and two-sided p-value will be summarized. Other variance-covariance structures may be substituted if convergence problems arise.

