4. STUDY ENDPOINTS

4.1. Efficacy

The primary efficacy endpoint is:

- Percent change from baseline in liver fat at Week 12, as determined by MRI-PDFF.

The key secondary efficacy endpoint is:

- The percentage of subjects with at least a 30% reduction in liver fat at Week 12, as determined by MRI-PDFF.

Additional secondary efficacy endpoints are:

- Percent change from baseline in liver fat at End of Treatment and End of Study, as determined by MRI-PDFF.

Sponsor: Sagimet Biosciences

Protocol Number: 3V2640-CLIN-005

Version and Date: Final Version 1, 02June2020

- Percentage of subjects with at least a 30% reduction in liver fat at End of Treatment and End of Study, as determined by MRI-PDFF.
- Change from baseline over the treatment period in:
 - Liver aminotransferases.
 - Lipid and lipoprotein parameters.
 - NASH and fibrosis markers.
 - Eicosanoids.

Exploratory efficacy endpoints are:

- Change from baseline over the treatment period in:
 - Liver fibrosis, as determined by VCTE.
 - Metabolic parameters.
 - Anthropometric parameters.
 - Lipidomic analyses for DNL.
- Proportion of subjects with <5% liver fat (normalized) at Week 12.

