8.3.2. Secondary Efficacy Endpoints and Analyses

MRI-PDFF Endpoints

Week 12 data for the secondary efficacy endpoints will be handled similarly to the handling used for the primary efficacy endpoint. That is, analyses will be performed both excluding data from subjects who required extended dosing beyond 12 weeks and including data from the extended dosing subjects as supplemental analyses.

The key secondary efficacy endpoint is the percentage of subjects with at least a 30% reduction in liver fat at Week 12, as determined by MRI-PDFF. Note that due to data collection precision, subjects with a reduction of at least 29.5% from baseline will count as responders. Differences between each TVB-2640 dose group (25 mg, 50 mg) and pooled placebo for the key secondary efficacy endpoint will be analyzed using CMH methods. The key secondary efficacy analyses will be based on a CMH test in the mITT population to compare each TVB-2640 dose group with placebo, adjusting for the stratification factor (diabetes presence/absence). For the final end

Sponsor: Sagimet Biosciences
Protocol Number: 3V2640-CLIN-005
Version and Date: Final Version 1, 02June2020

of study analysis, if a country-by-treatment interaction is found in the primary efficacy endpoint, the subjects from the US and China in the 50 mg cohort will be analyzed separately for the key secondary efficacy endpoint.

To check for other possible interactions, i.e., diabetes strata-dependent treatment effects, the Breslow-Day test will be performed; if the p-value of the Breslow-Day test is ≥ 0.05 , the treatment-by-strata interaction is deemed not significant. However, if the interaction effect is statistically significant (i.e., p value < 0.05), then the Gail and Simon test will be used to test for the qualitative interaction at a significance level of 0.05 and provided as an aid for interpretation of the CMH results. The estimated response rates and the corresponding exact 95% confidence interval based on a binomial distribution will be calculated for each treatment group. The exact 95% confidence limit for the CMH estimate of the common risk difference will also be obtained; a Wald asymptotic approximation with continuity correction is an acceptable substitute for the exact limits in the event of computational difficulties.

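### Read literally, SAP Appendix 1 takes extended-dosing subjects out of the ALT/AST and lipid comparisons for a reason that fits only measures taken after Week 12, and other SAP sections point the other way

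*SAP*

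**What the plan says.** SAP Appendix 1 cites uncertainty about what dosing beyond Week 12 does to efficacy, and concludes that "the primary and secondary efficacy analyses will be performed excluding subjects who entered extended dosing beyond 12 weeks". These subjects return only in a second tier: "Sensitivity analyses that include these subjects will be performed to evaluate the end of treatment efficacy". The rule removes subjects, not late samples, and names no endpoint.

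SAP 4.1 lists, as additional secondary efficacy endpoints, "Change from baseline over the treatment period in" liver aminotransferases, lipids and lipoproteins, NASH and fibrosis markers, and eicosanoids.

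SAP 8.3.2 has two parts. The first, headed for MRI-PDFF endpoints, says "Week 12 data for the secondary efficacy endpoints will be handled similarly to the handling used for the primary efficacy endpoint", and then that "analyses will be performed both excluding data from subjects who required extended dosing beyond 12 weeks and including data from the extended dosing subjects", the latter as supplemental. The second, on other efficacy endpoints, assigns ALT, AST and lipids to the as-treated population with a mixed model for repeated measures (MMRM). It states no exclusion of extended-dosing subjects.

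Protocol 13.2.2 says that for other continuous secondary endpoints "the changes at 12 weeks will be summarized for each treatment group and compared between each randomized TVB-2640 dose group and pooled placebo", using a repeated-measures model in the ITT population. It has no such exclusion either.

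For subjects dosed past Week 12, Protocol 7.1 provides for "planning for blood sample collection at an alternate site or home visit at Week 12", with a further sample on the last dosing day. Footnote 11 to the schedule of events adds: "Liver aminotransferases collected as part of the clinical chemistry panel for safety are also applicable for efficacy assessments".

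**The concern.** The reason given for the exclusion fits the MRI endpoint. A subject who extended has a scan after Week 12, under longer exposure than the endpoint intends. It does not fit visit-based blood endpoints, because extension begins only after Week 12. Samples at Weeks 2, 4 and 8, and a Week 12 sample where one was drawn, come from the same planned regimen as everyone else's.

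If the programmer follows Appendix 1, those samples leave the main between-group efficacy comparison with no gain in validity. The loss is defined by a post-randomisation condition (still on drug past Week 12). Among the randomised cohorts it falls only on Cohort 2, since footnote 2 to the schedule of events records the 25 mg cohort as already complete. If the programmer follows SAP Section 7 and the second part of 8.3.2, the samples stay. The plan should not leave that choice open.

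**Working it through.** **1. Samples an extended-dosing subject should have by Week 12** (protocol Table 2 and Section 7.1)

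- ALT/AST: baseline, Weeks 2, 4 and 8 as scheduled; Week 12 from the planned home or alternate-site draw, usable for efficacy under footnote 11.
- Lipid panel: baseline, Weeks 2, 4 and 8 as scheduled. Nothing says that the Week 12 home or alternate-site draw includes this panel.
- Eicosanoids: baseline and Week 4 before Week 12. SAP 8.3.2 makes these descriptive only.
- NASH/fibrosis markers: baseline, then nothing on treatment before Week 12. If that panel is not drawn at Week 12, there is no on-treatment value to keep.

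The point therefore rests mainly on ALT/AST through Week 12 and lipids through Week 8.

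**2. The SAP texts side by side**

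| SAP place | What it implies for extended-dosing subjects in the blood endpoints |
|---|---|
| Appendix 1 | Excluded from all secondary efficacy analyses; included only in sensitivity analyses |
| Section 7, general rules | All data to completion or withdrawal are analysed, whatever the treatment duration |
| 8.3.2, first part | Excluded in one analysis, included in a supplemental one, but under an MRI-PDFF sub-heading |
| 8.3.2, second part | As-treated population, MMRM, no exclusion stated |

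As-treated membership does not by itself override Appendix 1. The mITT definition also admits these subjects, yet SAP 8.3.1.1 excludes them from the primary analysis.

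**3. Do the sensitivity analyses recover the Week 12 sample?** Not clearly. They target End of Treatment, which SAP 3.1 allows up to Week 16 for these subjects, so the last-dosing-day sample is the natural candidate. SAP 7.7 analyses nominal visits without date windows and limits the use of unscheduled visits. A Week 12 home draw entered as unscheduled would therefore fall outside the by-visit model.

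**4. Size, under assumed counts.** The SAP says only that several subjects were affected. Take the planned US numbers (30 on 50 mg, 30 pooled placebo of which 15 are in Cohort 2), equal variance and one value per subject. The standard error is proportional to √(1/n_active + 1/n_placebo).

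- None lost: √(1/30 + 1/30) = 0.2582.
- 3 of 45 lost (2 active, 1 placebo): √(1/28 + 1/29) = 0.2649; ratio 0.2649/0.2582 = 1.026.
- 9 of 45 lost (6 active, 3 placebo): √(1/24 + 1/27) = 0.2805; ratio 0.2805/0.2582 = 1.087.
- Wide upper bound, 18 of 45 lost (12 active, 6 placebo): √(1/18 + 1/24)/0.2582 = 1.208.

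The 25 mg comparison loses only placebo subjects. With 3 lost, √(1/30 + 1/27)/0.2582 = 1.027.

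These ratios treat each lost subject as a complete record. Where an extended-dosing subject has no Week 12 value, keeping Weeks 2 to 8 recovers only part of the loss. No figure stated in the plan is in dispute here.

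**The case against.** The best reply is that the SAP already means what the fix asks for. Wherever its main text restricts these subjects, it does so for liver fat: the primary analysis (8.3.1.1), the analysis of persistence after treatment (8.3.1.2) and the MRI-PDFF part of 8.3.2. The blood endpoints have their own part of 8.3.2, with no exclusion and essentially the protocol's model. Section 7 includes all data. The Appendix 1 sentence follows a paragraph chiefly about late scans and can be read in that light.

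Much of this stands. A reader might infer from Appendix 1 that the SAP definitely drops these subjects from every blood-based endpoint. The documents do not support that, because they conflict. Nor is the first sentence of 8.3.2 independent support, given its sub-heading.

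Three further inferences also fail:

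- That the data are discarded. Appendix 1 keeps these subjects in all safety analyses, and SAP 8.5.2 summarises ALT and AST changes by visit with confidence intervals.
- That a primary objective is weakened. ALT and AST appear in the primary safety objective, which those safety analyses serve. The disputed rule concerns them as additional secondary efficacy endpoints, outside the fixed testing sequence.
- That bias is shown. The stated cause of extension is pandemic disruption, and neither the number nor any link to outcome is given.

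What the reply does not remove is the wording of Appendix 1. It is explicit and unrestricted, and it is the section that 8.3.1.1 points to for COVID-19 data handling.

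**Conclusion.** The point holds as a conflict with a practical consequence, and is worth a cheap correction. Read literally, Appendix 1 excludes extended-dosing subjects from the main ALT/AST and lipid MMRM on grounds that apply only to measures taken after Week 12. Section 7 and both parts of 8.3.2 point to a narrower rule. If Appendix 1 governs, on-drug samples at Weeks 2, 4 and 8, and Week 12 ALT/AST where drawn, leave the main efficacy comparison while remaining in the safety summaries and the End of Treatment sensitivity analyses.

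The cost is about 3% to 9% on the standard error of 50 mg versus pooled placebo if 3 to 9 of 45 US Cohort 2 subjects are affected. Those counts are assumptions. The verdict also assumes that the planned Week 12 draw took place and was already in the protocol version (6.0) on which the SAP is based. It does not assume that Week 12 lipid or biomarker values exist for these subjects. Neither the primary MRI-PDFF analysis nor the primary safety objective is affected.

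**What to change.** - In Appendix 1, limit the exclusion to MRI-PDFF endpoints and to other measures with no on-treatment value at or before Week 12.
- In the other-endpoints part of SAP 8.3.2, state that extended-dosing subjects stay in the main MMRM with all samples through Week 12, and that only samples taken after Week 12 are left out of the Week 12 analysis.
- In SAP 7.7, add one rule mapping the Week 12 home or alternate-site draw to nominal Week 12, and the last-dosing-day draw to End of Treatment.
- Reconcile Section 7, both parts of 8.3.2 and Appendix 1 so that one rule applies, and keep the End of Treatment analysis as supplementary.
- Report the number of extended-dosing subjects by arm.

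The cost is SAP wording and one mapping rule, with no new data collection. The downside is small: some Week 12 samples come from alternate sites, and panels not drawn there stay missing and are handled by the MMRM under its missing-at-random assumption.
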